10.3 Sample Size Calculation

The sample size calculation is based on the primary endpoint of feasibility only. The primary hypothesis is that the proportion of the patients who have OCT imaging which adds 5 minutes or less to the duration of standard of care colonoscopy is greater than 75%. The null hypothesis for feasibility is 75% and the alternative hypothesis is 90%. $H_0: p < 75\%$ $H_a: p > 75\%$ (expect it to be 90% in clinical practice). A sample size of 54 patients achieves 80.1% power to detect a difference of 15% using a two-sided exact test at a significance level of 5% with the assumption that the proportion is 75%.

10.4 Accrual

We perform screening and surveillance colonoscopies in about 10-15 patients per day at Barnes Jewish Hospital with similar characteristics and estimate approximately 5-10 patients/day may be eligible for and will participate in this trial. We anticipate enrolling our goal of 54 patients in about 3-4 weeks.

10.5 Statistical Analyses

10.5.1 Patient Disposition

The number of patients discontinued, the reasons for discontinuation, and the duration of OCT imaging administered will be summarized by patient and by reason for discontinuation.

10.5.2 Protocol Deviations

All significant deviations will be summarized by patient and by type of deviation.

10.5.3 Demographics and Baseline Characteristics

Subject demographic and clinical characteristics will be summarized to characterize the population. Descriptive summaries will include means, standard deviations, medians, ranges for continuous variables and frequency and percentage for categorical variables. They are presented by total and each arm, respectively.

10.5.4 Endpoint Analysis

Proportions of the patients whose procedure length using an OCT probe during routine colonoscopy is within 5 minutes and who have good OCT images, as judged by a machine learning algorithm, will be provided. Their associated 95% confidence intervals (CIs) will be calculated assuming a binomial distribution. The descriptive statistics will be presented including frequency, type, and severity of AEs related to OCT imaging during routine colonoscopy. Weighted kappa and 95% CI will be computed for the agreement between OCT imaging and pathology for all enrolled patients. All analyses will be conducted using SAS (SAS Institute, Cary, NC) at the two-sided 5% significance level.

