1.4 Risk/Benefit Assessment

1.4.1 Known Potential Risks

Known potential risks include added procedure sedation time as a result of OCT

imaging. We expect each polyp to be imaged within the span of 3 minutes and do not expect adding more than 5 minutes to total procedure time. Risk of infection and bleeding is <1% in standard of care colonoscopy. We don't expect the OCT probe to increase these risks. A table of common adverse events during a routine colonoscopy (with rates in percentages) is presented below. Adverse event rates in this study will be compared to the historic AE rates from this table.

Adverse Events 30 days After Outpatient Screening or Follow-Up Colonoscopy [31]

	Screening	Surveillance	No Polypectomy	Polypectomy
Death	0.03%	0.06%	0.02%	0.05%
Perforation	0.04%	0.12%	0.03%	0.07%
Hemorrhage	0.27%	0.38%	0.08%	0.50%
Diverticulitis	0.18%	0.22%	0.18%	0.20%
Abdominal pain	2.64%	2.21%	2.62%	2.56%
Any serious adverse event*	0.47%	0.68%	0.27%	0.74%
Hospitalizations	1.11%	1.61%	0.94%	1.43%
Emergency Department or Urgent Care Visit	2.26%	3.01%	2.23%	2.47%

*Serious adverse events include perforation, hemorrhage, or diverticulitis.

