2.0 OBJECTIVES AND ENDPOINTS

Objectives	Endpoints
Primary	
To demonstrate the procedural feasibility of OCT during routine colonoscopy	Whether a lesion can be adequately evaluated with OCT within 5 minutes during a standard of care colonoscopy.
Secondary	
To describe safety of OCT probe during routine colonoscopy	Adverse events related to OCT imaging during routine colonoscopy
To evaluate the quality of OCT images using a machine learning algorithm.	Whether OCT image is successfully captured using machine learning algorithm
To explore the diagnosis agreement between OCT imaging and pathology when a lesion is biopsied.	Weighted kappa

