6.0 REGULATORY AND REPORTING REQUIREMENTS

The entities providing oversight of safety and compliance with the protocol require reporting as outlined below. Please refer to Appendix A for definitions and Appendix B for a grid of reporting timelines.

Adverse events will be tracked from time of colonoscopy through 48 hours after end of colonoscopy. All adverse events must be recorded on the toxicity tracking case report form (CRF) with the exception of:

- Baseline adverse events, which shall be recorded on the medical history CRF

Refer to the data submission schedule in Section 7 for instructions on the collection of AEs in the EDC.

Reporting requirements for Washington University study team may be found in Section 6.1.

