10.2 Endpoints

Primary endpoint is whether a lesion can be adequately evaluated with OCT within 5 minutes during a standard of care colonoscopy. If the proportion of the patients whose procedure length using an OCT probe during routine colonoscopy is within 5 minutes is greater than 75%, then the feasibility is defined in this study.

Secondary endpoints include:

- AEs related to OCT imaging during routine colonoscopy
- Whether OCT image is successfully captured using machine learning algorithm, coded as “good” or “noisy”. The OCT imaging catheter will be calibrated before each patient study to ensure that the catheter system is working properly. In an in vivo study of the catheter, we expect some images will be distorted due to patient movement, sub-optimal contact with the mucosa, etc. The machine learning algorithm will judge image quality based on number of colonic crypts visualized (see Section 12, Figure 5). We hypothesize that the proportion of good OCT images is greater than 90%.
- Weighted Kappa. Clinical pathology is the gold standard for diagnosis. Diagnosis from both OCT and clinical pathology will be assigned as normal mucosa, hyperplastic polyp, tubular adenoma, sessile serrated adenoma, or colorectal cancer. Based on ex vivo data from [name] lab, we hypothesize that there will be an over 80% agreement rate in this feasibility study.

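### The planned safety summary covers only AEs judged related to OCT, but the protocol promises a comparison with a historic table not limited by cause, and does not say which study rate is used

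*Combined protocol and SAP*

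**What the plan says.** The safety endpoint is limited by attribution wherever it is stated. The Protocol Summary and Section 2.0 give it as "Adverse events related to OCT imaging during routine colonoscopy", and Section 10.2 as "AEs related to OCT imaging during routine colonoscopy". The analysis in Section 10.5.4 has the same limit: "The descriptive statistics will be presented including frequency, type, and severity of AEs related to OCT imaging during routine colonoscopy".

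Section 1.4.1 commits to a comparison: "Adverse event rates in this study will be compared to the historic AE rates from this table". The table is titled "Adverse Events 30 days After Outpatient Screening or Follow-Up Colonoscopy". Its columns are screening, surveillance, no polypectomy and polypectomy. Nothing in its title, rows or footnote limits events by cause. Section 10.5 does not mention the comparison.

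Collection is wider than analysis. Section 6.0 states: "All adverse events must be recorded on the toxicity tracking case report form (CRF) with the exception of" baseline events, which go on the medical history form. Section 7.1 repeats this for everything from colonoscopy onward, and Section 5.3 sets the window at 48 hours. Section 9.0 and Appendix B send toxicities to the monitoring committee without limiting them to related events.

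**The concern.** A rate of events judged to be caused by the probe and a rate of events after colonoscopy from any cause do not measure the same thing. The first leaves out the background that makes up the second. Set side by side, the study can look as safe as history, or safer, while the total event rate has risen.

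The design makes this harder to detect. The study is one-arm and unblinded, so no control group can show an excess that attribution misses. Imaging takes place within the colonoscopy (Section 5.2), so colonoscopy, sedation, imaging and any polypectomy share one session. Apart from pointing to outside definitions in Appendix A, the documents give no rule for separating these causes. A bleed at a polyp that was imaged and then removed could reasonably be put down to the removal.

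At stake is the secondary objective of describing safety, and any statement that AE rates compare well with history.

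**Working it through.** The plan gives no sample size, power or expected count for safety (Section 10.3 sizes the study on feasibility only), so there is no safety figure to reproduce.

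**Inputs.** N = 54 (Section 10.3). About 40 patients with polyps (Section 5.2), leaving 54 − 40 = 14. Rates from the Section 1.4.1 table.

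**Step 1: background implied by the table.** Expected count = 40 × polypectomy rate + 14 × no-polypectomy rate, assuming every polyp patient has a polypectomy.

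- Abdominal pain: 40 × 2.56% + 14 × 2.62% = 1.39
- Emergency or urgent-care visit: 40 × 2.47% + 14 × 2.23% = 1.30
- Hospitalization: 40 × 1.43% + 14 × 0.94% = 0.70
- Any serious AE: 40 × 0.74% + 14 × 0.27% = 0.33

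These are 30-day counts. The 48-hour background cannot be derived from the documents.

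**Step 2: when a related-only rate falls below history.** Let b be the background rate, e the excess due to the probe, f the share of background attributed to OCT and g the share of excess attributed. The expected related-only rate is f·b + g·e, which is below b when g·e < (1 − f)·b. With f = 0 and g = 1, any excess smaller than b is hidden (up to 100% of background). With f = 0 and g = 0.5, any excess smaller than 2b is hidden (up to 200%).

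**Step 3: size in 54 patients.** Take abdominal pain at the screening rate, b = 2.64%, so 54 × 2.64% = 1.43 expected. The study rate is below history with at most 1 event (1/54 = 1.85%; 2/54 = 3.70%). The table shows the expected count and the exact binomial P(X ≤ 1). It assumes that b applies in full within the study and that f = 0.

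| True rate | All-cause | Related-only, g = 1 | Related-only, g = 0.5 |
|---|---|---|---|
| b (no effect) | 1.43; 58% | 0; 100% | 0; 100% |
| 2b | 2.85; 21% | 1.43; 58% | 0.71; 84% |
| 3b | 4.28; 7% | 2.85; 21% | 1.43; 58% |

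**Step 4: the window.** Suppose the probe adds nothing and a share w of the 30-day background falls within 48 hours (w is an assumption). All-cause expected counts are 1.43w: 1.43, 0.71 and 0.36 for w = 1, 0.5 and 0.25. The chance of falling below history is 58%, 84% and 95%. All-cause counting removes the attribution bias but not this one.

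**Step 5: precision.** For 0 of 54, the two-sided exact 95% upper limit is 1 − 0.025^(1/54) = 6.6%. For 0 of 40 it is about 8.8%, and for 0 of 14 about 23%. With 0.33 serious AEs expected, P(none) = (1 − 0.0074)^40 × (1 − 0.0027)^14 ≈ 72%, even counting all causes. An exact one-sided 5% test of all-cause abdominal pain against 2.64% needs 5 or more events and has about 16% power for a doubling.

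**The case against.** The strongest reply is that the documents never say related-only rates will be set against the table. A reader might infer from Sections 1.4.1 and 10.5.4 together that a biased comparison is planned. Section 1.4.1 speaks of AE rates in the study without restriction, and Section 10.5.4 does not mention the comparison. This stands: the defect is an unspecified numerator. But if all-cause rates are meant, no analysis produces them, and the same edit is needed.

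A reader might also infer that unrelated AEs go unreported. They do not: all AEs are recorded and reach the monitoring report. What is missing is narrower, namely an all-cause summary in the endpoint analysis.

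Nor do the figures show that the study rate must look low. One related serious AE is 1/54 = 1.85%, above every serious-AE rate in the table (0.27% to 0.74%). If abdominal pain tripled and all the excess were attributed, 2.85 related events would be expected against 1.43.

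On attribution, Section 1.4.1 itself names added sedation time as a consequence of OCT imaging, and the table has no sedation row, so sedation events do not bear on this comparison. Appendix A sets a threshold of reasonable possibility for a suspected reaction, so a bleed at an imaged polyp need not be excluded. Misattribution is a risk, not a finding.

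Finally, the objective is only to describe safety, no safety test is planned, and 54 patients cannot settle the matter. That limits what any comparison can show. It does not justify setting a filtered rate against an unfiltered one.

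**Conclusion.** The concern holds in this form: the endpoint and its only planned analysis cover OCT-related AEs, the protocol promises a comparison with a table not limited by cause, and which study rate enters it is left open. If the related-only rates are used, the study rate is biased low. In the abdominal-pain illustration with a doubled rate, the chance of appearing below history rises from 21% to between 58% and 84%.

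Those percentages assume that the 30-day screening rate applies in full within the study and that no background event is attributed to OCT. The Step 1 counts also assume that every polyp patient has a polypectomy. They show direction and rough size; they do not forecast the study's result. The 48-hour window against 30 days is a separate mismatch in the same direction, and it remains even when all causes are counted. This should be corrected before analysis, because it changes what the safety comparison can be taken to mean.

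**What to change.** In Section 10.5.4, summarise all AEs from colonoscopy to 48 hours regardless of attribution, by frequency, type and grade, with exact 95% confidence intervals. Give them overall and, descriptively, by polypectomy and no polypectomy to match the table's columns. Keep OCT-related AEs as a subset table.

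In Section 1.4.1, state that:

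- only the all-cause rates are set against the historic table;
- the comparison is descriptive;
- the study's 48 hours are shorter than the table's 30 days, so a lower study rate cannot be read as evidence of no added harm.

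The serious-event row should be tallied by the table's own footnote (perforation, hemorrhage or diverticulitis), which is narrower than the Appendix A definition of an SAE.

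The cost is a few sentences and one extra table from AEs already collected. Polypectomy status must be available for each patient; the documents do not list the fields of the Colonoscopy Procedure Form, so this should be confirmed. The headline AE rate will be higher than the OCT-related rate, and the intervals will be wide, particularly for the group of about 14 without polyps.

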10.6 Early Stopping Rules

Toxicity, defined as study-related grade 3-5 SAEs, will be reviewed on a continuous basis. Early stopping will be based on the toxicity rate (TR) using the repeated significance testing of Pocock boundary with 80% power and 0.05 overall Type I error. We assume that no more than 5% is acceptable and a maximum-tolerated TR is 30%. The study will be halted if a study-related grade 3-5 SAE occurs in the first 2 patients, or 2 of the first 8 patients, or 3 of the first 15 patients, or 4 of the first 24 patients, or 5 of the first 34 patients,

or 6 of the first 45 patients. R function-toxbdry was used for calculations.

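### The listed safety stopping counts do not have the stated 0.05 type I error or 80% power: false-halt probability at a 5% toxicity rate is 9.6% or 15.9%, depending on how the first entry is read

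*Combined protocol and SAP*

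**What the plan says.** Section 10.6 (Early Stopping Rules) defines toxicity as study-related SAEs of grade 3 to 5, which "will be reviewed on a continuous basis". Stopping is based on the toxicity rate, "using the repeated significance testing of Pocock boundary with 80% power and 0.05 overall Type I error". The two reference rates follow: "We assume that no more than 5% is acceptable and a maximum-tolerated TR is 30" per cent.

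The boundary begins: "The study will be halted if a study-related grade 3-5 SAE occurs in the first 2 patients, or 2 of the first 8 patients". It continues with 3 in 15, 4 in 24 and 5 in 34, and ends "or 6 of the first 45 patients". On the source of these counts the section says only that "R function-toxbdry was used for calculations". It gives neither the arguments of that call nor the operating characteristics of the resulting list. Section 5.2 sets enrolment at 54 participants.

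**The concern.** The section gives both the error rates and the boundary, so one can be checked against the other. The list looks too permissive for an overall 0.05: with a 5% event rate, 2 events among 8 patients is not a rare outcome, and it is only one of six ways to halt.

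The first entry is also unclear. Every other entry has the form of k events in n patients. The first, "The study will be halted if a study-related grade 3-5 SAE occurs in the first 2 patients", gives no count. Read literally, one SAE in either of the first two patients halts the study. Read as 2 of 2, in line with the other entries, both patients must have one.

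This is the protocol's only numerical safety halting rule, and Section 9.0 requires the semi-annual report to the monitoring committee to cover it with supporting data. If the stated error rate is wrong, the committee is told a false-halt risk that the rule does not have. If the first entry is unclear, the investigators cannot tell what a single early event requires of them.

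**Working it through.** **Inputs.** From Section 10.6: acceptable rate 5%; maximum tolerated rate 30%; stated type I error 0.05 and power 80%; boundary points (events, patients) of (1 or 2, 2), (2, 8), (3, 15), (4, 24), (5, 34) and (6, 45). From Section 5.2: 54 patients.

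**Method.** Let X be the cumulative number of patients with a qualifying SAE, each occurring independently with probability p. At patient k the study halts if X is at least r, where r is the smallest listed count whose patient number is k or more. The distribution of X among paths not yet halted is updated one patient at a time, P(X = x after k) = (1 − p)·P(X = x after k − 1) + p·P(X = x − 1 after k − 1), and any mass at or above r is moved to the halted state. Type I error is the halted mass at p = 0.05; power is the halted mass at p = 0.30.

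**Step 1: a single entry settles the type I question.** For 2 or more events in 8 patients at 5%:

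1 − 0.95^8 − 8 × 0.05 × 0.95^7 = 1 − 0.6634 − 0.2793 = 0.0572 (unrounded terms).

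One of the six entries already exceeds the stated overall 0.05. The first entry, if it means one event, is larger still: 1 − 0.95² = 0.0975. If it means two events it is 0.05² = 0.0025.

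**Step 2: the full list at a 5% rate.** Cumulative halt probability by the end of each segment:

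| Through entry | First entry = 1 of 2 | First entry = 2 of 2 |
|---|---|---|
| 2 patients | 0.0975 | 0.0025 |
| 8 patients | 0.1271 | 0.0572 |
| 15 patients | 0.1389 | 0.0721 |
| 24 patients | 0.1476 | 0.0825 |
| 34 patients | 0.1541 | 0.0901 |
| 45 patients | 0.1594 | 0.0962 |

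A simulation of 200,000 trials gave 0.1590 and 0.0958.

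**Step 3: other true rates.**

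| True rate | First entry = 1 of 2 | First entry = 2 of 2 | Stated |
|---|---|---|---|
| 5% | 0.1594 | 0.0962 | 0.05 |
| 15% | 0.7984 | 0.7737 | – |
| 30% | 0.9986 | 0.9984 | 0.80 |

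Read backwards, the list gives a 5% halt probability at a true rate of about 2.1% (1 of 2) or 3.8% (2 of 2), and 80% at about 15.0% or 15.5%.

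**Step 4: attempts to recover the stated figures.** Reviewing only at the listed sample sizes changes nothing, because the cumulative count never falls. Ending at 45 instead of 54 patients changes nothing, because no entry lies beyond 45. Adding a point of 7 events for patients 46 to 54 raises the type I error to 0.1619 or 0.0990. The only variant tried that falls below 0.05 is halting on one more event than each listed count (2/2, 3/8, 4/15, 5/24, 6/34, 7/45). It gives 0.0198 and 0.9937, which is not the stated pair and contradicts the printed wording.

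**Step 5: shape.** A Pocock boundary uses a roughly constant pointwise level. The listed counts have pointwise tails at 5% of 0.0975 (if 1 of 2), 0.0572, 0.0362, 0.0298, 0.0259 and 0.0239, about a fourfold fall. With each count one higher, the last five tails are nearly flat, between 0.0055 and 0.0067. That pattern would fit counts printed one too low, but this is inference: the documents do not give the call.

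**The case against.** The type I mismatch is hard to dispute; the case on the other side is that it matters little.

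- **Power.** More than 99% at a 30% rate satisfies an 80% requirement if 80% is a minimum. This stands. It is a misdescription, not a loss of protection.
- **Realistic rates.** Section 1.4.1 gives 30-day rates of 0.27% to 0.74% for any serious adverse event and 0.94% to 1.61% for hospitalization. The rule counts only study-related grade 3 to 5 SAEs within 48 hours. At 0.74% the list halts with probability 1.6% (1 of 2) or 0.2% (2 of 2); at 2%, with 4.7% or 1.2%. This stands too: at the rates the protocol expects, a false halt is uncommon.
- **Direction.** The list halts sooner than stated, so participants are not under-protected. Enrolment is expected to take 3 to 4 weeks (Section 10.4), and the sample size for the primary endpoint is untouched. This stands.
- **Size of the ambiguity.** The 9.75% is the stand-alone probability of at least one event in two patients. Changing the reading moves the overall figure from 9.6% to 15.9%, a difference of 6.3 points. This is the fairer measure of what the wording alone decides.
- **Cause.** The documents do not show whether the counts, the wording or the stated error rates are at fault. This limits what can be prescribed.

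None of this removes the contradiction. The plan itself chose 5% and 30% as the rates at which its error probabilities are stated, and the list misses both.

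**Conclusion.** The concern holds. At the protocol's own acceptable rate of 5%, the listed rule halts with probability 15.9% or 9.6%, about three or two times the stated 0.05, and no reading of the first entry gives 0.05. At 30% it halts with probability 99.9% or 99.8%, not 80%. The type I error is the substantive fault; the power figure is an overshoot. The ambiguous first entry is a separate defect of wording with a direct operational consequence.

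The figures assume independent events with a constant probability per patient, up to 54 patients, each outcome known before the next count is assessed, and halting on reaching a listed count. They do not depend on whether review is continuous or only at the listed sample sizes. The correction must be made before the rule is relied on, although the practical risk of a false halt is small if the true rate is near the background rates in Section 1.4.1.

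**What to change.** Reconcile the three parts of Section 10.6: the listed counts, the wording of the first entry and the stated error rates. The documents do not show which is at fault, and this review does not say which halting rule is right. The sponsor should:

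1. Retrieve the original toxbdry call and compare its output with the printed counts; report the arguments used.
2. If the printed counts are the intended ones, replace the stated error rates with those the list has: type I error of about 10% or 16% at 5%, according to the reading of the first entry, and power above 99% at 30%. If the stated 0.05 is the intended design, rerun the boundary at that level and replace the list.
3. State whether the first entry means one or two events, in the same form as the other entries.
4. Add a short table of halt probability by true toxicity rate, including the background rates of Section 1.4.1 as well as 5% and 30%.

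The cost is one rerun of the function and a paragraph of wording. If the list is kept, the stated type I error becomes less favourable.

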1.4.2 Known Potential Benefits

There is no direct benefit to the patient. We hope that this feasibility study will answer the question of whether or not this OCT probe is feasible in routine colonoscopy. This may lead to another study of assessing the diagnostic accuracy of the OCT probe.

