6.1 WU PI Reporting Requirements

6.1.1 Reporting to the Human Research Protection Office (HRPO) at Washington University

Reporting will be conducted in accordance with Washington University IRB Policies.

Pre-approval of all protocol exceptions must be obtained prior to implementing the change.

6.1.2 Reporting to the Quality Assurance and Safety Monitoring Committee (QASMC) at Washington University

The PI (or designee) is required to notify the QASMC of any unanticipated problems involving risks to participants or others occurring at WU or any BJH or SLCH institution that has been reported to and acknowledged by HRPO. (Unanticipated problems reported to HRPO and withdrawn during the review process need not be reported to QASMC.)

QASMC must be notified within **10 days** of receipt of IRB acknowledgment via email to [contact]. Submission to QASMC must include the myIRB form and any supporting documentation sent with the form.

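### The safety stopping rule accepts a 5% rate of study-related grade 3-5 SAEs with no link to the protocol's own colonoscopy risk figures, and reaches an 80% chance of halting only at a true rate near 15%

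*Combined protocol and SAP*

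**What the plan says.** Section 10.6 (Early Stopping Rules) monitors study-related grade 3-5 SAEs continuously. Its two rates appear without a source: "We assume that no more than 5% is acceptable and a maximum-tolerated TR is 30" percent. The method is a "Pocock boundary with 80% power and 0.05 overall Type I error". The printed rule halts for an event in the first 2 patients, 2 of 8, 3 of 15, 4 of 24, 5 of 34 or 6 of 45. No step is printed for patients 46 to 54.

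Section 1.4.1 (Known Potential Risks) describes the background: "Risk of infection and bleeding is <1% in standard of care colonoscopy", and the probe is not expected to add to this. Of its table it says: "Adverse event rates in this study will be compared to the historic AE rates from this table". Over 30 days the table gives 0.47% (screening), 0.68% (surveillance), 0.27% (no polypectomy) and 0.74% (polypectomy) for any serious adverse event, and 1.11%, 1.61%, 0.94% and 1.43% for hospitalizations. Its footnote limits the first of these rows: "Serious adverse events include perforation, hemorrhage, or diverticulitis".

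Section 6.0 sets the observation window: "Adverse events will be tracked from time of colonoscopy through 48 hours after end of colonoscopy". Section 1.4.2 states: "There is no direct benefit to the patient".

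**The concern.** An acceptable rate in a stopping rule is the level of harm at which the study should usually carry on. For an imaging add-on that offers the patient nothing directly, one expects that level to be argued from the known risk of the underlying procedure. Section 1.4.1 supplies that risk and names it as the comparator, but Section 10.6 does not use it or explain a departure from it.

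This is the only rate threshold for safety in the plan. If it is lax, a device problem that raised study-related SAEs well above anything Section 1.4.1 anticipates could run through most or all of the 54 patients without triggering a halt. For instance, events in patients 3, 9, 16, 25 and 35 cross no printed limit, and a sixth in patient 46 meets none. At the table's highest serious-event figure, one would expect 54 × 0.0074 = 0.40 all-cause events over 30 days.

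**Working it through.** **Inputs.** N = 54 (Sections 5.2 and 10.3); the printed limits and the 5%, 30% and 0.05 figures (Section 10.6); the table rates (Section 1.4.1). The true rate of 7.4% is an illustration, ten times the highest serious-event figure (10 × 0.74%). The 10% unacceptable rate is also an assumption.

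**Readings.** The first printed entry can mean at least one event in the first 2 patients (reading A) or an event in both (reading B, already covered by 2 of 8). Ranges below span the two.

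**Formula.** Let b(i) be the smallest k whose limit n_k is at or beyond patient i, and a_i(s) the probability of s events after i patients without a halt. Then a_i(s) = a_{i-1}(s)(1-p) + a_{i-1}(s-1)p for s < b(i), and zero otherwise. P(halt) = 1 - Σ_s a_54(s). Expected patients imaged = Σ_{i=1..54} Σ_s a_{i-1}(s).

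**The plan's own figures first.** At p = 5% the first step of reading A alone has probability 1 - 0.95² = 0.0975. For reading B, 2 of 8 alone has 1 - 0.95⁸ - 8(0.05)(0.95)⁷ = 0.057. Each already exceeds 0.05. Over the whole rule P(halt) at 5% is 0.159 (A) or 0.096 (B), so the stated type I error is not reproduced. At 30% it is 0.9986 or 0.9984, well above the stated 80% power.

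**Printed rule against recalibrated rules.** Recalibrated means a constant pointwise level, the largest keeping overall P(halt) at or below 0.05 at the acceptable rate p0, N = 54. The limits are:

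- p0 = 5%: 2/4, 3/11, 4/20, 5/30, 6/41, 7/52, 8/54
- p0 = 1.61%: 1/1, 2/14, 3/36, 4/54
- p0 = 1%: 1/2, 2/25, 3/54

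| True rate | Printed, B to A | p0 = 5% | p0 = 1.61% | p0 = 1% |
|---|---|---|---|---|
| 0.74% | 0.002-0.016 | <0.001 | 0.013 | 0.031 |
| 1.61% | 0.008-0.036 | 0.002 | 0.050 | 0.110 |
| 5% | 0.096-0.159 | 0.050 | 0.395 | 0.580 |
| 7.4% | 0.235-0.302 | 0.163 | 0.663 | 0.811 |
| 10% | 0.433-0.489 | 0.362 | 0.851 | 0.932 |
| 15% | 0.774-0.798 | 0.750 | 0.979 | 0.993 |

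The true rate at which P(halt) = 0.80 is 15.0% (A) or 15.5% (B) for the printed rule, 15.9% for p0 = 5%, 9.1% for p0 = 1.61% and 7.2% for p0 = 1%.

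**Patients imaged at a true 7.4%.** Printed rule 40.9 (A) to 45.1 (B); p0 = 1.61%, 32.7; p0 = 1%, 26.8.

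**Sensitivity.** Adding a 7-of-54 step to the printed rule moves its 80% point to 14.2-14.7%. Carrying 6 events through patient 54 raises halting at 10% to 54-58%. Neither changes the conclusion.

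**The case against.** The best defence is that a tolerance limit may properly sit above background, and that the table is not a like-for-like benchmark. Its rows are all-cause over 30 days, while Section 10.6 counts only study-related grade 3-5 SAEs and events are tracked for 48 hours. The below-1% statement covers infection and bleeding only. Section 1.4.1 makes the table a comparator for study results, not a halting threshold. This stands as far as it goes: ratios of 5% to the table rows should not be read as a measured excess. But restricting to study-related events and to 48 hours both push the expected countable rate down. The one difference in the other direction, that Appendix A seriousness includes hospitalization, is met by using the hospitalization row.

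The rule does react to gross harm (94-95% at a true 20%, above 99.8% at 30%). The absolute saving is modest: at 7.4%, the 1% rule spares 40.9 - 26.8 = 14 to 45.1 - 26.8 = 18 patients, or about 1.0 to 1.35 SAEs. Other safeguards exist: the investigator "is required to notify the QASMC of any unanticipated problems involving risks to participants or others" (Section 6.1.2), and Section 9.0 requires ongoing monitoring. None of these sets a rate.

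Three stronger readings are tempting and are not supported:

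- **That the printed counts follow from the 5% input.** They do not. They halt 9.6-15.9% of the time at 5%, and a true 5% boundary is looser.
- **That the 30% had little effect on the counts.** The documents do not show how it entered the calculation, and no calculation here varies it.
- **That the six-monthly timing of the monitoring report leaves patients unprotected.** Section 10.6 review is continuous, so that timing does not delay a halt.

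**Conclusion.** The point holds as a design weakness that should be corrected. The 5% acceptable and 30% maximum-tolerated rates are unexplained and out of line with the protocol's own account of risk. As printed, the rule is more likely to continue than to halt at a true study-related SAE rate of 10%, and it needs 15.0-15.5% before halting is 80% likely. Correcting the calibration while keeping 5% would make this slightly worse (15.9%), which is why the acceptable rate has to change.

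The result rests on 54 patients, independent events at a constant rate, limits applied as printed, and either reading of the first entry. The exact rate to adopt is a judgement. That Section 1.4.1 implies a figure well below 5% does not depend on which of its rows is used.

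**What to change.** Re-run the Pocock boundary for N = 54 at overall alpha 0.05 with an acceptable rate taken from Section 1.4.1 and about 10% as unacceptable. Replace the limits in Section 10.6, carry them through patient 54, state the first entry as a count out of a number of patients, and print the derivation with halt probabilities at several true rates. Two workable choices:

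- **1.61% acceptable** (highest hospitalization figure): halt at 1 of 1, 2 of 14, 3 of 36 or 4 of 54. Halts 5% of the time at 1.61%, 66% at 7.4% and 85% at 10%.
- **1% acceptable** (the infection and bleeding statement): halt at 1 of 2, 2 of 25 or 3 of 54. Halts 5% at 1%, 81% at 7.4% and 93% at 10%.

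A 10% unacceptable rate is within reach of 54 patients: even with 2% acceptable, the boundary has 80% power there. The sponsor and the QASMC may settle on nearby values.

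The cost is one re-run and replacement text, with no added patients. The downside is more halts without a device effect: 1.3% (1.61% rule) or 3.1% (1% rule) at a true 0.74%, and 5% or 11% at 1.61%, against 0.2-1.6% and 0.8-3.6% for the printed rule. In practice these should be lower, because only study-related events within 48 hours count.
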